### **Serious infections**

Any events like this will be listed under cluster = Infections, and can be identified based on AESER = Y

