A similar summary table will be produced for all TEAEs including those of the parent trials (C201 and C202). Any event happening either on parent trial or on the current trial will be considered for deriving the number and percentage of subjects with at least one event, and the number of events. The incidence per 100 patient years will be calculated as:  $100 \times (\text{Number of subjects with AE}) / (\text{Total number of years observed starting from the first dose in parent trial, summed for all subjects})$ .

Another summary table will be presented selecting adverse events of special interest. Search criteria for these adverse events can be found in section 16.5.

The following categories will be included in the summary table:

- infection
- serious infection (requiring hospitalization or i.v. antimicrobial treatment)
- opportunistic infection, excluding TB
- active TB infection
- latent TB infection
- Herpes zoster infection
- malignancy
- hypersensitivity reaction (including anaphylaxis and angioedema)
- hypersensitivity reaction (including anaphylaxis and angioedema) leading to withdrawal
- GI perforation
- demyelinating disorder
- MACE

This table will represent events which occurs only after the first dose of study drug in C203 study.

One more summary table for AEs of special interest will be produced including events from the parent trials as well. Any event happening either on parent trial or on the current trial will be considered for deriving the number and percentage of subjects with at least one event, and the number of events. The incidence per 100 patient years will be calculated as:  $100 \times (\text{Number of AEs}) / (\text{Total number of years observed starting from the first dose in parent trial, summed for all subjects})$ .

Tables by SOC and PT will report the number and percentage of subjects with at least one event, occurring only after the first dose of study drug on C203 study. Percentages will be calculated out of the number of subjects in the relevant treatment group.

These tables will be prepared for the following selections of AEs:

- TEAEs
- TEAEs by severity (Mild, Moderate, Severe)
- TEAEs with an incidence of at least 3%
- serious TEAEs
- non-serious TEAEs
- study drug-related TEAEs
- study procedure-related TEAEs
- TEAE for which the study or the study drug were discontinued

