## 16.5 Appendix 5: Search criteria for adverse events of special interest

Search criteria for AESIs are either MedDRA PT clusters or SMQs. The SMQs and the individual PTs for the PT clusters are provided below. The MedDRA version used for the data coding is v21.0.

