Typhoid carrier	Urinary bladder abscess	Vaccine associated paralytic poliomyelitis
Typhoid fever	Urinary tract abscess	Vaccine breakthrough infection
Typhus	Urinary tract infection	Vaccine virus shedding
Typhus rickettsia test	Urinary tract infection bacterial	Vaccinia test positive
Typhus rickettsia test positive	Urinary tract infection enterococcal	Vaccinia virus infection
Ulcerative keratitis	Urinary tract infection fungal	Vaginal abscess
Umbilical hernia gangrenous	Urinary tract infection neonatal	Vaginal cellulitis
Umbilical sepsis	Urinary tract infection pseudomonal	Vaginal infection
Upper aerodigestive tract infection	Urinary tract infection staphylococcal	Vaginitis chlamydial
Upper respiratory fungal infection	Urinary tract infection viral	Vaginitis gardnerella
Upper respiratory tract infection	Urinary tract inflammation	Vaginitis viral
Upper respiratory tract infection bacterial	Urogenital infection bacterial	Variant Creutzfeldt-Jakob disease
Upper respiratory tract infection helminthic	Urogenital infection fungal	Varicella
Urachal abscess	Urogenital infection trichomoniasis	Varicella post vaccine
Ureaplasma infection	Urosepsis	Varicella virus test
Ureaplasma test positive		Varicella virus test positive
Ureter abscess		Varicella zoster gastritis

Vector-borne transmission of infection	Viral sepsis	Vulvovaginitis streptococcal
Veillonella infection	Viral sinusitis	Vulvovaginitis trichomonal
Veillonella test positive	Viral skin infection	
Vertical infection transmission	Viral test	Waterhouse-Friderichsen syndrome
Vessel puncture site infection	Viral test positive	Weil's disease
Vestibular neuronitis	Viral titre	West Nile viral infection
Vestibulitis	Viral titre decreased	Whipple's disease
Vibrio test positive	Viral titre increased	Withdrawal hepatitis
Viraemia	Viral tonsillitis	
Viral cardiomyopathy	Viral tracheitis	Wound abscess
Viral corneal ulcer	Viral upper respiratory tract infection	Wound contamination
Viral diarrhoea	Viral uveitis	Wound infection
Viral epiglottitis	Viral vasculitis	Wound infection bacterial
Viral haemorrhagic cystitis	Virologic failure	Wound infection fungal
Viral hepatitis carrier	Visceral larva migrans	Wound infection helminthic
Viral infection	Visceral leishmaniasis	
Viral labyrinthitis	Vitreous abscess	Wound infection pseudomonas
Viral load	Vitritis	Wound infection staphylococcal
Viral load decreased	Vorticella infection	
Viral load increased	Vulval abscess	Wound infection viral

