### **Opportunistic infections (excluding TB)**

Aeromonas infection	Candida endophthalmitis	Cytomegalovirus chorioretinitis
Aeromonas test positive	Candida osteomyelitis	Cytomegalovirus colitis
Allescheriosis	Candida pneumonia	Cytomegalovirus duodenitis
Alternaria infection	Candida retinitis	
Aspergilloma	Candida sepsis	Cytomegalovirus enteritis
Aspergillosis oral	Capnocytophaga infection	Cytomegalovirus enterocolitis
Aspergillus infection	Capnocytophaga test positive	Cytomegalovirus gastritis
Aspergillus test	Cerebral aspergillosis	Cytomegalovirus gastroenteritis
Aspergillus test positive	Cerebral fungal infection	Cytomegalovirus gastrointestinal infection
Atypical mycobacterial lower respiratory tract infection	Cerebral toxoplasmosis	Cytomegalovirus gastrointestinal ulcer
Atypical mycobacterial pneumonia	Chronic pulmonary histoplasmosis	Cytomegalovirus hepatitis
Atypical mycobacterium pericarditis	Coccidioides encephalitis	Cytomegalovirus infection
Bacillary angiomatosis	Coccidioidomycosis	Cytomegalovirus mucocutaneous ulcer
BK virus infection	Colitis herpes	Cytomegalovirus myelomeningoradiculitis
Bronchopulmonary aspergillosis	Cryptococcal cutaneous infection	Cytomegalovirus myocarditis
Burkholderia cepacia complex infection	Cryptococcal fungaemia	Cytomegalovirus oesophagitis
Burkholderia cepacia complex sepsis	Cryptococciosis	Cytomegalovirus pancreatitis
Burkholderia gladioli infection	Cryptococcus test positive	
Burkholderia infection	Cryptococcus test positive	
Burkholderia test positive	Cutaneous coccidioidomycosis	

Cytomegalovirus pericarditis	Gastroenteritis cryptococcal	Herpes zoster meningoencephalitis
Cytomegalovirus syndrome	Genital herpes zoster	Herpes zoster meningomyelitis
Cytomegalovirus test	Hepatic candidiasis	
Cytomegalovirus test positive	Hepatic infection fungal	Herpes zoster necrotising retinopathy
Cytomegalovirus urinary tract infection	Hepatitis toxoplasmal	Herpes zoster oticus
Cytomegalovirus viraemia	Hepatosplenic candidiasis	Herpes zoster pharyngitis
Disseminated cryptococcosis	Herpes oesophagitis	Histoplasmosis cutaneous
Disseminated cytomegaloviral infection	Herpes sepsis	Histoplasmosis disseminated
Encephalitis cytomegalovirus	Herpes simplex colitis	Infection in an immunocompromised host
Encephalitis fungal	Herpes simplex encephalitis	JC polyomavirus test
Endocarditis histoplasma	Herpes simplex gastritis	JC polyomavirus test positive
Enterocolitis fungal	Herpes simplex hepatitis	JC virus granule cell neuronopathy

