Oesophageal candidiasis	Proctitis herpes	Varicella zoster gastritis
Ophthalmic herpes zoster	Progressive multifocal leukoencephalopathy	Varicella zoster oesophagitis
Opportunistic infection	Progressive vaccinia	Varicella zoster pneumonia

Adrenal gland tuberculosis	Male genital tract tuberculosis	Tuberculosis liver
Bone tuberculosis	Meningitis tuberculous	Tuberculosis of central nervous system
Choroid tubercles	Oesophageal tuberculosis	Tuberculosis of eye
Congenital tuberculosis	Pericarditis tuberculous	Tuberculosis of genitourinary system
Conjunctivitis tuberculous	Peritoneal tuberculosis	Tuberculosis of intrathoracic lymph nodes
Cutaneous tuberculosis	Prostatitis tuberculous	Tuberculosis of peripheral lymph nodes
Disseminated tuberculosis	Pulmonary tuberculoma	Tuberculosis ureter
Ear tuberculosis	Pulmonary tuberculosis	Tuberculous abscess
Epididymitis tuberculous	Renal tuberculosis	central nervous system
Erythema induratum	Salpingitis tuberculous	Tuberculous endometritis
Exposure to communicable disease	Silicotuberculosis	Tuberculous laryngitis
Extrapulmonary tuberculosis	Spleen tuberculosis	Tuberculous pleurisy
Female genital tract tuberculosis	Thyroid tuberculosis	Tuberculous tenosynovitis
Joint tuberculosis	Tuberculosis of central nervous system	
Lymph node tuberculosis	Tuberculosis	
	Tuberculosis bladder	
	Tuberculosis gastrointestinal	

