### Latent TB

Latent tuberculosis	Mycobacterium tuberculosis complex	Tuberculin test false negative
Mycobacterium test positive		Tuberculin test positive

Herpes zoster infection		
Colitis herpes	Herpes zoster	Herpes zoster meningoencephalitis
Gastritis herpes	Herpes zoster cutaneous disseminated	Herpes zoster meningomyelitis
Genital herpes zoster	Herpes zoster disseminated	Herpes zoster necrotising retinopathy
Herpes oesophagitis	Herpes zoster infection neurological	Herpes zoster oticus
Herpes ophthalmic		
Herpes pharyngitis	Herpes zoster meningitis	Herpes zoster pharyngitis
Herpes sepsis		
Herpes virus infection		

Meningitis herpes  
Meningomyelitis herpes  
Ophthalmic herpes  
zoster  
Pneumonia herpes viral  
Proctitis herpes  
Varicella zoster gastritis  
Varicella zoster  
oesophagitis  
Varicella zoster  
pneumonia  
Varicella zoster virus  
infection

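### Serious infections are drawn only from the Infections term list, which lacks up to six terms held in the SAP's own opportunistic and zoster lists, so a serious event coded to one of them would miss the infection rows

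*SAP*

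**What the plan says.** SAP 7.1 plans a summary table of adverse events of special interest in which infection, serious infection, opportunistic infection excluding TB, active TB, latent TB and herpes zoster are separate rows. The rows feed Table 14.3.1.3 (events after the first C203 dose) and Table 14.3.1.4 (parent-trial events included).

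Appendix 5 (16.5) supplies the search criteria and presents the lists as operative: "The SMQs and the individual PTs for the PT clusters are provided below". Infections, opportunistic infections, active TB, latent TB and herpes zoster are each given as a list of preferred terms (PTs). Serious infection has no list, only a rule: "Any events like this will be listed under cluster = Infections, and can be identified based on AESER = Y".

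The SAP does not say that the infection row is the union of these lists. Protocol 3.4.4.1 asks the investigator to mark whether an event is a serious infection, but the SAP does not say that this mark is used to build the row.

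**The concern.** The rule has a hidden premise: that every infection PT in the narrower lists is also in the Infections list. If one is not, a serious event coded to it satisfies the seriousness flag but fails the cluster filter. The rows then stop nesting. A table could show a serious opportunistic or zoster event that is in neither the infection row nor the serious-infection row beside it.

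This matters because protocol 1.2.5 names infection as a risk of blocking the IL-6 pathway, and serious infection is the row a safety reader will look at first. Results are also split over the eight parent-arm groups of SAP 4.2.2, where one case can be the difference between 0 and 1.

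**Working it through.** The plan gives no figure to reproduce. The check is a comparison of lists, all from SAP 16.5.

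**Step 1: size of the lists.** The opportunistic list has 201 distinct terms and the herpes zoster list has 27. They share 22, so the union is 201 + 27 − 22 = 206. Two apparent spelling variants (*Cryptococciosis*, *cheloneae*) were counted as matches.

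**Step 2: terms not found in Infections.**
- Opportunistic list: 5 of 201.
- Zoster list: 3 of 27.
- Two terms are in both sets, so 5 + 3 − 2 = 6 distinct terms are absent. That is 6/206 = 2.9%; the other 200 (97.1%) are present.

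**Step 3: the six terms and their surroundings.**

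| Term | Listed under | What Infections shows at that place |
|---|---|---|
| "Cytomegalovirus gastrointestinal ulcer" | Opportunistic | Passes from CMV gastrointestinal infection to CMV hepatitis, mid-column |
| *Exserohilum test* | Opportunistic | Passes from Exserohilum infection to External ear cellulitis, mid-column |
| *Exserohilum test positive* | Opportunistic | Same place |
| *Varicella zoster oesophagitis* | Opportunistic and zoster | Last varicella entry is "Varicella zoster gastritis", then a page break, then Vector-borne transmission of infection |
| "Varicella zoster pneumonia" | Opportunistic and zoster | Same place |
| *Varicella zoster virus infection* | Zoster | Same place |

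Four of the six are diseases and two are test names.

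**Step 4: could the varicella gap be lost text?** The number of printed lines in the three columns on that page was estimated under two assumed fonts and several column widths. The last column came out 2 to 5 lines shorter than its neighbours, and the three terms would need about 6 lines. Loss of one or two of them when the page was read cannot be excluded. The CMV and Exserohilum gaps lie inside columns and do not depend on this.

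**Step 5: what is captured.** Of the 25 CMV terms in the opportunistic list, 24 are in Infections, including colitis, hepatitis and pneumonia. All 12 terms that contain the words herpes zoster are there too. Of the four varicella-zoster terms, one (gastritis) is there.

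**Step 6: active TB.** The only term in that block not found in Infections is *Exposure to communicable disease*, which is an exposure and not an infection.

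**Step 7: size per missed event.** The documents give no patient-years, so this rests on an assumption. If all 501 subjects were followed for the maximum 114 weeks:
- 501 × 114 = 57,114 subject-weeks; 57,114 / 52.18 ≈ 1,095 patient-years.
- One missed event: 100 / 1,095 ≈ 0.09 per 100 patient-years.
- At half that follow-up: about 0.18 per 100 patient-years.

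These figures are for the overall column of Table 14.3.1.3. Table 14.3.1.4 adds parent-trial time to the denominator, so one missed event weighs less there.

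**The case against.** The strongest objection is that these are gaps in the reading of a PDF and not gaps in the plan. Three of the four disease terms sit exactly at a page break. The appendix is also visibly garbled within columns: *Respirovirus test positive* appears four times running and *Postoperative wound infection* three times. A dropped *Cytomegalovirus gastrointestinal ulcer* beside a near-identical neighbour is conceivable. This stands as a reason to check the source page, and for the varicella terms the point is conditional on that check. It is less convincing as a full explanation. Agreement is otherwise 97%, and two adjacent Exserohilum terms are missing together in mid-column. One missing disease term is enough to make the premise false.

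A second objection is that no event disappears. Protocol 3.4.4.1 and 3.5.2 require every serious infection to be reported as an SAE, so it would appear in Table 14.3.1.8 and Listing 16.2.7.2 as well as in the opportunistic or zoster row. That is correct, and it limits the consequence to the infection and serious-infection rows.

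A reader might infer from the gaps that serious visceral zoster or CMV disease is left out in general. Step 5 shows otherwise: only events coded to the named terms are affected. A reader might also infer that the serious-infection row is always biased downward. The omitted terms can only lower it, but the Infections list also holds terms that are not infections, such as *Adiponectin increased* and *Guillain-Barre syndrome*, and a serious event coded to one of those would raise it. The documents do not settle the net direction.

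**Conclusion.** As written, the rule rests on a premise that the SAP's own lists contradict. At least one disease term and two test terms in the opportunistic list are outside the cluster from which serious infections are selected. Up to three varicella-zoster terms join them if the source page confirms the gap. The infection rows are therefore not guaranteed to contain the rows that should nest within them.

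The expected effect is small. Events coded to these terms are rare, and one missed event would shift the overall rate in Table 14.3.1.3 by about 0.09 to 0.18 per 100 patient-years under the follow-up assumed above. A percentage loss in the serious-infection count cannot be stated without assuming both a serious-infection rate and that a missed case has occurred, and the documents supply neither. The lists also do not show whether each of the six is a current term in the stated dictionary ("The MedDRA version used for the data coding is v21.0"); if one is not, no event can be coded to it.

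The case for change is one of correctness and nesting, not of a large expected bias.

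**What to change.** First compare the six terms with the source page of the Infections list. Then replace the rule in SAP 16.5 with a definition that does not depend on one list being complete:

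- *Infection*: any PT in the Infections, opportunistic, active TB or herpes zoster list, leaving out pure exposure terms such as *Exposure to communicable disease*.
- *Serious infection*: AESER = Y within that set.
- *Programming check*: every event in the opportunistic, active TB and herpes zoster rows, other than the excluded exposure terms, must also be in the infection row.

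Adding only the four disease terms to the Infections list is not equivalent. The two Exserohilum test terms would still be outside, and the check could fail. Cleaning the whole Infections list of non-infection terms is a separate and larger task, and this point does not require it.

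The cost is a short change to the text of 16.5, a changed PT filter and one check in the code for Tables 14.3.1.3 and 14.3.1.4. No new data are needed. The downside is that infection and serious-infection counts may rise slightly.

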### **Opportunistic infections (excluding TB)**

Aeromonas infection	Candida endophthalmitis	Cytomegalovirus chorioretinitis
Aeromonas test positive	Candida osteomyelitis	Cytomegalovirus colitis
Allescheriosis	Candida pneumonia	Cytomegalovirus duodenitis
Alternaria infection	Candida retinitis	
Aspergilloma	Candida sepsis	Cytomegalovirus enteritis
Aspergillosis oral	Capnocytophaga infection	Cytomegalovirus enterocolitis
Aspergillus infection	Capnocytophaga test positive	Cytomegalovirus gastritis
Aspergillus test	Cerebral aspergillosis	Cytomegalovirus gastroenteritis
Aspergillus test positive	Cerebral fungal infection	Cytomegalovirus gastrointestinal infection
Atypical mycobacterial lower respiratory tract infection	Cerebral toxoplasmosis	Cytomegalovirus gastrointestinal ulcer
Atypical mycobacterial pneumonia	Chronic pulmonary histoplasmosis	Cytomegalovirus hepatitis
Atypical mycobacterium pericarditis	Coccidioides encephalitis	Cytomegalovirus infection
Bacillary angiomatosis	Coccidioidomycosis	Cytomegalovirus mucocutaneous ulcer
BK virus infection	Colitis herpes	Cytomegalovirus myelomeningoradiculitis
Bronchopulmonary aspergillosis	Cryptococcal cutaneous infection	Cytomegalovirus myocarditis
Burkholderia cepacia complex infection	Cryptococcal fungaemia	Cytomegalovirus oesophagitis
Burkholderia cepacia complex sepsis	Cryptococciosis	Cytomegalovirus pancreatitis
Burkholderia gladioli infection	Cryptococcus test positive	
Burkholderia infection	Cryptococcus test positive	
Burkholderia test positive	Cutaneous coccidioidomycosis	

Cytomegalovirus pericarditis	Gastroenteritis cryptococcal	Herpes zoster meningoencephalitis
Cytomegalovirus syndrome	Genital herpes zoster	Herpes zoster meningomyelitis
Cytomegalovirus test	Hepatic candidiasis	
Cytomegalovirus test positive	Hepatic infection fungal	Herpes zoster necrotising retinopathy
Cytomegalovirus urinary tract infection	Hepatitis toxoplasmal	Herpes zoster oticus
Cytomegalovirus viraemia	Hepatosplenic candidiasis	Herpes zoster pharyngitis
Disseminated cryptococcosis	Herpes oesophagitis	Histoplasmosis cutaneous
Disseminated cytomegaloviral infection	Herpes sepsis	Histoplasmosis disseminated
Encephalitis cytomegalovirus	Herpes simplex colitis	Infection in an immunocompromised host
Encephalitis fungal	Herpes simplex encephalitis	JC polyomavirus test
Endocarditis histoplasma	Herpes simplex gastritis	JC polyomavirus test positive
Enterocolitis fungal	Herpes simplex hepatitis	JC virus granule cell neuronopathy
Exserohilum infection	Herpes simplex meningitis	JC virus infection
Exserohilum test	Herpes simplex meningoencephalitis	Kaposi's sarcoma AIDS related
Exserohilum test positive	Herpes simplex meningomyelitis	Kaposi's varicelliform eruption
Eye infection toxoplasmal	Herpes simplex necrotising retinopathy	Listeria encephalitis
Fungaemia	Herpes simplex oesophagitis	Listeria sepsis
Fungal abscess central nervous system	Herpes simplex pneumonia	Listeria test positive
Fungal oesophagitis	Herpes simplex sepsis	Lymphadenitis fungal
Fungal retinitis	Herpes simplex visceral	Meningitis aspergillus
Fungal sepsis	Herpes zoster cutaneous disseminated	Meningitis candida
Fungal tracheitis	Herpes zoster disseminated	Meningitis coccidioides
Fusarium infection	Herpes zoster infection neurological	Meningitis cryptococcal
Gastritis fungal	Herpes zoster meningitis	Meningitis exserohilum
Gastritis herpes		Meningitis fungal
		Meningitis herpes

Meningitis histoplasma	Oral candidiasis	Pseudallescheria infection
Meningitis listeria	Oral fungal infection	Pseudallescheria sepsis
Meningitis toxoplasmal	Oral hairy leukoplakia	Pyelonephritis fungal
Meningomyelitis herpes	Oro-pharyngeal aspergillosis	Respiratory moniliasis
Methylobacterium infection	Oropharyngeal candidiasis	Retinitis histoplasma
Miliary pneumonia	Oropharyngitis fungal	Retinitis viral
Mucocutaneous candidiasis	Otitis media fungal	Rhodococcus infection
Mucormycosis	Pancreatitis fungal	Rhodococcus test positive
Mycobacterium avium complex immune restoration disease	Penicillium infection	Scedosporium infection
Mycobacterium avium complex infection	Pericarditis fungal	Sepsis pasteurella
Mycobacterium cheloneae infection	Pericarditis histoplasma	Sinusitis aspergillus
Mycobacterium fortuitum infection	Phaeohyphomycosis	Sinusitis fungal
Mycobacterium kansasii infection	Pneumocystis jirovecii infection	Splenic candidiasis
Myocarditis toxoplasmal	Pneumocystis jirovecii pneumonia	Splenic infection fungal
Necrotising herpetic retinopathy	Pneumocystis test positive	Stomatococcal infection
Neurocryptococcosis	Pneumonia cryptococcal	Stomatococcus test positive
Neutropenic infection	Pneumonia cytomegaloviral	Strongyloidiasis
Neutropenic sepsis	Pneumonia herpes viral	Systemic candida
Nocardia sepsis	Pneumonia toxoplasmal	Systemic mycosis
Nocardia test positive	Polyomavirus-associated nephropathy	Tonsillitis fungal
Nocardiosis	Presumed ocular histoplasmosis syndrome	Upper respiratory fungal infection
Oesophageal candidiasis	Proctitis herpes	Varicella zoster gastritis
Ophthalmic herpes zoster	Progressive multifocal leukoencephalopathy	Varicella zoster oesophagitis
Opportunistic infection	Progressive vaccinia	Varicella zoster pneumonia

Adrenal gland tuberculosis	Male genital tract tuberculosis	Tuberculosis liver
Bone tuberculosis	Meningitis tuberculous	Tuberculosis of central nervous system
Choroid tubercles	Oesophageal tuberculosis	Tuberculosis of eye
Congenital tuberculosis	Pericarditis tuberculous	Tuberculosis of genitourinary system
Conjunctivitis tuberculous	Peritoneal tuberculosis	Tuberculosis of intrathoracic lymph nodes
Cutaneous tuberculosis	Prostatitis tuberculous	Tuberculosis of peripheral lymph nodes
Disseminated tuberculosis	Pulmonary tuberculoma	Tuberculosis ureter
Ear tuberculosis	Pulmonary tuberculosis	Tuberculous abscess
Epididymitis tuberculous	Renal tuberculosis	central nervous system
Erythema induratum	Salpingitis tuberculous	Tuberculous endometritis
Exposure to communicable disease	Silicotuberculosis	Tuberculous laryngitis
Extrapulmonary tuberculosis	Spleen tuberculosis	Tuberculous pleurisy
Female genital tract tuberculosis	Thyroid tuberculosis	Tuberculous tenosynovitis
Joint tuberculosis	Tuberculosis of central nervous system	
Lymph node tuberculosis	Tuberculosis	
	Tuberculosis bladder	
	Tuberculosis gastrointestinal	

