HIV wasting syndrome	Hydrocele male infected	Infected dermal cyst
HIV-associated neurocognitive disorder	Hymenolepisis	Infected fistula
Hookworm infection	Hypopyon	Infected lymphocele
Hordeolum	Iatrogenic infection	Infected naevus
HTLV test positive	Ileal gangrene	Infected neoplasm
HTLV-1 carrier	Immune reconstitution inflammatory syndrome associated tuberculosis	Infected seroma
HTLV-1 test positive	Impetigo	Infected skin ulcer
HTLV-2 test positive	Implant site abscess	Infected varicose vein
Human anaplasmosis	Implant site cellulitis	Infection
Human ehrlichiosis	Implant site infection	Infection in an immunocompromised host
Human herpes virus 6 serology	Implant site pustules	Infection masked
Human herpes virus 6 serology positive	Incision site abscess	Infection parasitic
Human herpes virus 8 test positive	Incision site cellulitis	Infection protozoal
Human herpesvirus 6 infection	Incisional hernia gangrenous	Infection reactivation
Human herpesvirus 7 infection	Inclusion body myositis	Infection susceptibility increased
Human herpesvirus 8 infection	Inclusion conjunctivitis	Infection transmission via personal contact
Human immunodeficiency virus transmission	Inclusion conjunctivitis neonatal	Infection via vaccinee
Human papilloma virus test	Indeterminate leprosy	Infectious colitis
Human papilloma virus test positive	Indirect infection transmission	Infectious crystalline keratopathy
		Infectious disease carrier
		Infectious iridocyclitis
		Infectious mononucleosis

Infectious pleural effusion	Influenza C virus test positive	Joint abscess
Infectious thyroiditis	Influenza virus test	Joint tuberculosis
Infective aneurysm	Influenza virus test positive	Kaposi's sarcoma AIDS related
Infective aortitis	Infusion site abscess	Kaposi's varicelliform eruption
Infective chondritis	Infusion site cellulitis	Kawasaki's disease
Infective corneal ulcer	Infusion site infection	Keratitis
Infective episcleritis	Infusion site pustule	Keratitis bacterial
Infective exacerbation of bronchiectasis	Inguinal hernia gangrenous	Keratitis fungal
Infective exacerbation of chronic obstructive airways disease	Injection site abscess	Keratitis interstitial
Infective gastroduodenitis	Injection site cellulitis	Keratitis viral
Infective glossitis	Injection site infection	Keratoconjunctivitis measles
Infective iritis	Injection site joint infection	Keratosis gonococcal
Infective mesenteric panniculitis	Injection site pustule	Kerion
Infective myositis	Instillation site abscess	Kidney infection

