Infective periostitis	Instillation site infection	Klebsiella bacteraemia
Infective pulmonary exacerbation of cystic fibrosis	Instillation site pustules	Klebsiella infection
Infective spondylitis	Intervertebral discitis	Klebsiella sepsis
Infective tenosynovitis	Intestinal fistula infection	Klebsiella test positive
Infective thrombosis	Intestinal gangrene	Kuru
Infective uveitis	Intestinal tuberculosis	Kyasanur Forest disease
Infestation	Intrauterine infection	Labyrinthitis
Influenza	Iridocyclitis	Lacrimal sac cellulitis
Influenza A virus test	Iritis	Lactobacillus infection
Influenza A virus test positive	Isosporiasis	Lactobacillus test positive
Influenza B virus test	Japanese spotted fever	Laryngitis
Influenza B virus test positive	JC polyomavirus test	Laryngitis bacterial
	JC polyomavirus test positive	Laryngitis fungal
	JC virus granule cell neuronopathy	Laryngitis viral
	JC virus infection	Laryngotracheitis obstructive
	Jejunal gangrene	Lassa fever

Latent syphilis	Lung abscess	Mastoid empyema
Latent tuberculosis	Lung infection	Mastoiditis
Legionella infection	Lung infection	Measles
Legionella test	pseudomonal	Measles antibody
Legionella test positive	Lupus encephalitis	Measles antibody positive
Leishmaniasis	Lupus vulgaris	Measles post vaccine
Lemierre syndrome	Lyme disease	Mediastinal abscess
Lentivirus test positive	Lymph gland infection	Mediastinitis
Lepromatous leprosy	Lymph node abscess	Meibomian gland discharge
Leprosy	Lymph node tuberculosis	Meibomianitis
Leptospira test positive	Lymphadenitis bacterial	Meningitis
Leptospirosis	Lymphadenitis fungal	Meningitis aseptic
Leptotrichia infection	Lymphadenitis	Meningitis aspergillus
Leuconostoc infection	helminthic	Meningitis bacterial
Lice infestation	Lymphadenitis viral	Meningitis borrelia
Ligneous conjunctivitis	Lymphangitis	Meningitis candida
Lineal gingival erythema	Lymphogranuloma	Meningitis chemical
Lip infection	venereum	Meningitis coccidioides
Listeria encephalitis	Lyssavirus test positive	Meningitis coxsackie
Listeria sepsis	Malaria	viral
Listeria test positive	Malaria antibody test	Meningitis cronobacter
Listeriosis	Malaria antibody test positive	Meningitis cryptococcal
Liver abscess	Malarial myocarditis	Meningitis echo viral
Localised infection	Male genital tract	Meningitis enterococcal
Lochial infection	tuberculosis	Meningitis enteroviral
Louping ill	Malignant syphilis	Meningitis eosinophilic
Lower respiratory tract infection	Marburg disease	Meningitis exserohilum

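### The fixed term lists behind the SAP's active-TB and opportunistic-infection rows are inconsistent: a non-TB exposure term counts as TB, some TB terms are left out, and the opportunistic list follows no visible rule

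*SAP*

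**What the plan says.** SAP 7.1 plans two summary tables of adverse events of special interest, one for C203 only (Table 14.3.1.3) and one including the parent trials (Table 14.3.1.4). Infection, serious infection, "opportunistic infection, excluding TB", active TB, latent TB and herpes zoster are separate rows.

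Appendix 5 (SAP 16.5) gives the operative definition: "Search criteria for AESIs are either MedDRA PT clusters or SMQs". The infection rows use printed preferred-term (PT) lists, one of them under a heading that begins "Opportunistic infections (excluding TB". For serious infections it states: "Any events like this will be listed under cluster = Infections, and can be identified based on AESER = Y". That row therefore depends on the Infections list.

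Neither SAP 7.1 nor Appendix 5 states a medical-review step that could move a case between rows. SAP section 11 (changes from the protocol) does not comment on the lists.

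**The concern.** When a closed list is the definition, an error in the list is a counting error. Four features look wrong.

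- An exposure term is counted as active TB.
- Some TB terms that the SAP itself classes as infections are missing from the TB block.
- The opportunistic list takes in mild or test-only terms and leaves out more serious relatives of the same kind.
- Some opportunistic terms are not in the Infections cluster, so a serious case coded to one would be missed by both the infection row and the serious-infection row.

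Infection is the first risk that Protocol 1.2.5 names for IL-6 pathway inhibition, and long-term safety is part of the study objective. These are rare-event rows, in which one case can turn a zero into a one. The protocol schedules TB questioning at Week 0 and from Week 12 onward, so a report of exposure is a plausible entry.

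**Working it through.** The plan gives no figure to reproduce. The check compares the printed lists, then works out what one misplaced case would do.

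**1. Active-TB block.** Its heading is lost in the extracted text. It is read as active TB from its content and its place between the opportunistic and latent-TB lists, which matches the row order in SAP 7.1. It prints 44 entries, 43 distinct.

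- In the block but not in Infections: one term, "Exposure to communicable disease".
- In Infections but not in the block: "Intestinal tuberculosis", *Bovine tuberculosis* and "Immune reconstitution inflammatory syndrome associated tuberculosis". The block does count "Tuberculosis gastrointestinal".
- *Tuberculoma of central nervous system* also appears to be missing, but the block prints *Tuberculosis of central nervous system* twice, once at the alphabetical place of the tuberculoma term. That is probably a misread, so it is not counted here.

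**2. Opportunistic list.** It prints 202 entries, 201 distinct. Related terms from the SAP's own lists, side by side:

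| Counted as opportunistic | In Infections, not counted as opportunistic |
|---|---|
| *Tonsillitis fungal*, *Sinusitis fungal* | *Pneumonia fungal* |
| *Listeria test positive* | *Listeriosis* |
| *M. avium* complex, *chelonae*, *fortuitum* and *kansasii* infections | *Mycobacterium abscessus infection* |
| *Chronic pulmonary histoplasmosis* | *Acute pulmonary histoplasmosis* |
| *Endocarditis histoplasma* | *Fungal endocarditis* |

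These are examples. *Osteomyelitis fungal*, *Central nervous system fungal infection*, *Histoplasmosis* and *Toxoplasmosis* are also left out. No total is claimed, because the SAP gives no rule against which to count.

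**3. Opportunistic terms absent from Infections.** Two spelling variants (*Cryptococciosis*, *cheloneae*) are accepted as matches. Five of 201 entries are then not found (5/201 = 2.5%):

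- *Cytomegalovirus gastrointestinal ulcer*, *Exserohilum test* and *Exserohilum test positive*. These gaps fall mid-column. They are 3/201 = 1.5%.
- *Varicella zoster oesophagitis* and *Varicella zoster pneumonia*. These fall at a page break, where *Varicella zoster virus infection* (printed in the herpes zoster list) is missing too. A run of neighbouring terms lost at one break is probably a reading loss, so these two are set aside.

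**4. Where a case would go under the lists as printed.**

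- Intestinal TB: counted as infection, and as serious infection if serious; not as active TB.
- Exposure report: counted as active TB; not as infection.
- Serious cytomegalovirus gastrointestinal ulcer: counted as opportunistic; not as infection or serious infection.

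**5. Size per case, all-subjects column of Table 14.3.1.3.** Inputs are the planned maximum of about 501 subjects and the maximum duration of 114 weeks (protocol synopsis).

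- Percentage: 1/501 = 0.20%.
- Patient-years at most: 501 × 114 / 52.18 = 1,095.
- Rate: 100 × 1/1,095 = 0.09 per 100 patient-years.

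Both steps are minimums, because enrolment and follow-up can only be lower. Steps within a single treatment group are larger, but group sizes are not given.

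**The case against.** The strongest objection is that much of this is proof by absence from damaged lists. The Infections list used as comparator repeats entries (*Postoperative wound infection* three times running, *Respirovirus test positive* four times), so rows may have been overwritten. Whether an omitted term is a codable PT needs MedDRA v21.0, which is not in the documents. This stands as a condition: every absence must be confirmed before the lists are edited. It does not touch the exposure term, which is printed in the block.

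Second, what counts as opportunistic is clinical judgement, and the SAP does not say that the clusters must nest. This also stands in part, since some omissions may be deliberate. But no rationale is given, and a rule that admits a positive listeria test and excludes listeriosis is hard to construct. Of the three firm non-nested terms two are test terms, so the risk to the serious-infection row rests mainly on one term.

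Third, safeguards exist. Serious infections are reported as SAEs, verbatim and preferred terms are listed for every event, TB requires stopping study drug (Protocol 3.2.3.2), and a DSMB monitors safety. This stands and limits the severity.

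A reader might infer that opportunistic or TB cases would vanish from the report, or that the infection risk is understated by a known amount. The documents support neither. Cases remain in the system-organ-class tables and listings, the error can run in both directions, and no case coded to these terms is shown.

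**Conclusion.** The concern holds at minor severity with medium confidence. As printed, the active-TB block counts one term that is not TB and omits three TB terms that the SAP treats as infections. The opportunistic list is internally inconsistent. At least three of its terms fall outside the cluster that feeds the serious-infection row.

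The size is at least about 0.2 percentage points and 0.09 per 100 patient-years for each misplaced case in the all-subjects column of Table 14.3.1.3. The number of such cases cannot be derived from the documents and may be zero. The analysis is descriptive, so no inference depends on it.

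The conclusion assumes that the unheaded block is the active-TB list, that the absences are real in the original PDF, and that the omitted terms are current PTs in MedDRA v21.0.

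**What to change.** Before database lock, after checking each term in the original PDF and in MedDRA v21.0:

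1. Remove *Exposure to communicable disease* from the active-TB cluster. Add *Intestinal tuberculosis*, *Bovine tuberculosis* and the immune-reconstitution TB term.
2. State one rule for what counts as opportunistic. Have the medical reviewer reconcile the whole Infections cluster, and all coded infection PTs, against the opportunistic list under that rule. Add at least *Pneumonia fungal*, *Listeriosis* and *Mycobacterium abscessus infection*.
3. Define the infection row as the union of the Infections, opportunistic, TB and herpes zoster clusters, excluding pure exposure terms, and select serious infections from that union.

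The cost is a list edit and a short review of terms already coded, with no new data. The downside is that opportunistic and TB counts may come out slightly higher.
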